4.2 METHOD OF TREATMENT ASSIGNMENT AND BLINDING

The investigator or the investigator's research staff will provide patient eligibility information through the interactive Web response system (IxRS) at randomization. Each patient will be randomized and assigned a unique identification number. As confirmation, the investigator will be provided with written verification of each patient's registration.

Patients will be randomized to receive obinutuzumab or placebo in a 1:1 ratio. Patients randomized to receive obinutuzumab will be further randomized to receive one of the two obinutuzumab dosing schedules (1000 mg IV on Day 1 and Weeks 2, 24, 26, 50 and 52; or 1000 mg IV on Day 1 and Weeks 2, 24, 26, and 52) in a 1:1 ratio. All patients will receive blinded infusions on Day 1 and Weeks 2, 24, 26, 50, and 52.

The randomization of patients into treatment and control groups will be managed by a central IxRS vendor by use of a block design. The factors for balancing between the treatment groups will be the following:

- Region
 - United States and Canada
 - Latin America and the Caribbean
 - Other
- Race
 - Black
 - Other

These stratification factors were selected given expected differences in response by region and race. LN is clinically heterogeneous in presentation and factors such as availability and intensity of standard of care therapies; socioeconomic status; and ethnicity are known to affect a patient's response to treatment (Tesar et al 2011). In particular, black race is associated with more aggressive disease (Korbet et al 2007).

Because it is important to maintain blinding to preserve the integrity of the data collected, all laboratory studies of blood specimens, with unblinding potential, will be performed by a central laboratory. Therefore, site personnel and the Sponsor's staff involved with the conduct of the study will not receive unblinded data related to peripheral B-cell counts, PK results, specific immunoglobulin levels (IgM, IgA), or ADA results during the study, as listed below, until the primary efficacy and safety analyses through Week 76.

While PK samples must be collected from patients assigned to the comparator arm to maintain the blinding of treatment assignment, PK assay results for these patients are generally not needed for the safe conduct or proper interpretation of this study. Sponsor personnel responsible for performing PK assays will be unblinded to patients' treatment assignments to identify appropriate PK samples to be analyzed. Samples from patients who are assigned to the comparator arm will not be analyzed except by request (e.g., to evaluate a possible error in dosing).

If emergency unblinding is necessary for patient management (e.g., in the case of a serious adverse event for which patient management might be affected by knowledge of treatment assignment), the investigator will be able to break the treatment code by contacting the IxRS. Treatment codes should not be broken except in emergency situations. If the investigator wishes to know the identity of the study treatment for any other reason (non-emergency unblinding), they should contact the Medical Monitor directly. If the Medical Monitor agrees to patient unblinding, the investigator will be able to break the treatment code by contacting the IxRS. The investigator should document and provide an explanation for any premature unblinding.

For regulatory reporting purposes and if required by local health authorities, the Sponsor will break the treatment code for all serious, unexpected suspected adverse reactions (see Section 5.7) that are considered by the investigator or Sponsor to be related to study drug.

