3.1.5 Study Unblinding

The primary efficacy and safety analyses will be performed after data is available for all patients through the Week 76 assessments or early study discontinuation. After the primary analysis the Sponsor will be unblinded to treatment assignment. In order to collect additional controlled data beyond Week 76 for those patients who have an adequate response, unblinding of investigators and patients will not occur until data is available for all eligible patients through one year of blinded follow-up beyond Week 76 and the analysis of data through this point has been completed.

Following study unblinding, blinded infusions will be discontinued, no further OLT will be initiated, and ongoing OLT will be completed after the OLT Week 52 infusion. Subsequently, patients will be referred to the Sponsor's continued access provision for obinutuzumab and MMF access (see Section 4.3.4) or enter SFU (see Section 3.1.4).

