4.5.4 Vital Signs

Vital signs will include measurements of respiratory rate, body temperature, pulse rate, and systolic and diastolic blood pressures while the patient is in a seated position for 5 minutes. Before, during, and after infusions, vital signs may also be collected while patient is in a semi-supine position. The same arm for blood pressure measurements should be used consistently throughout the study, if possible, and the position in which the blood pressure was taken should be documented in the eCRF. Record abnormalities observed at baseline on the General Medical History and Baseline Conditions eCRF. At subsequent visits, record new or worsened clinically significant abnormalities on the Adverse Event eCRF.

4.5.5 Laboratory, Biomarker, and Other Biological Samples

Samples for the following laboratory tests will be sent to one or several central laboratories for analysis (except where specified as a local laboratory test):

 Hematology: CBC, hemoglobin, hematocrit, RBC, mean corpuscular volume, mean corpuscular hemoglobin, WBC (absolute and differential), and quantitative platelet count

If a test is required to assess hemolytic anemia (e.g., the direct Coombs' test), it will be performed locally.

- Blood chemistry: AST/SGOT, ALT/SGPT, alkaline phosphatase, amylase (at screening only), lipase (at screening only), total protein, albumin, cholesterol, total bilirubin, BUN, uric acid, creatinine, random glucose, potassium, sodium, chloride, calcium, phosphorus, lactic dehydrogenase, CPK, cystatin C, and triglycerides
- Urinalysis: dipstick for blood, nitrite, protein, and glucose and urine microscopy
 Preferably, UPCR analysis should be performed on a first morning void (FMV) (see Appendix 3).
- 24-hour urine collection: total protein, total creatinine, and creatinine clearance, and UPCR (see Appendix 3)
- Flow cytometry: B cell (CD19), T cell (CD3, 4, 8) and NK cells (CD16, CD56) via TBNK assay; B-cells and subsets (including CD19, CD27, CD38, IgD) via HSFC

Flow cytometry results will remain blinded until the study is unblinded.

- Autoantibody profile (ANA, anti-dsDNA, anti-Sm, anti-RNP, anti-Ro, antiLa, antiC1q)
- Quantitative immunoglobulins: total, IgA, IgG, and IgM
- Complement: including C3, C4, and CH50
- Hemoglobin A_{1c}
- Antibody titers: Measurement of antibody titers to common antigens (mumps, Varicella, rubella, tetanus, and Streptococcus pneumoniae) will be performed according to the schedule of activities.

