Patients will be randomized to receive obinutuzumab or placebo in a 1:1 ratio. Patients randomized to receive obinutuzumab will be further randomized to receive one of the two obinutuzumab dosing schedules in a 1:1 ratio:

- Obinutuzumab Arm 1 (2-2-2 Regimen): absolute (flat) dose of 1000 mg IV on Day 1 and Weeks 2, 24, 26, 50, and 52
- Obinutuzumab Arm 2 (2-2-1 Regimen): absolute (flat) dose of 1000 mg IV on Day 1 and Weeks 2, 24, 26, and 52

All patients will receive blinded infusions on Day 1 and Weeks 2, 24, 26, 50, and 52.

The randomization of patients into treatment and control groups will be managed by a central IxRS vendor and will be performed by stratified block design—stratified by region and race as follows:

- Region
 - United States and Canada
 - Latin America and the Caribbean
 - Other
- Race
 - Black
 - Other

These stratification factors were selected given expected differences in response by region and race. LN is clinically heterogeneous in presentation and factors such as availability and intensity of standard of care therapies; socioeconomic status; and ethnicity are known to affect a patient's response to treatment (Tesar et al. 2011). In particular, black race is associated with more aggressive disease (Korbet et al. 2007).

Because it is important to maintain blinding to preserve the integrity of the data collected, all laboratory studies of blood specimens, with unblinding potential, will be performed by a central laboratory. Therefore, site personnel and the Sponsor's staff involved with the conduct of the study will not receive unblinded data related to peripheral B-cell counts, PK results, specific immunoglobulin levels, or ADA results during the study, as listed below, until the primary efficacy and safety analyses through Week 76.

While PK samples must be collected from patients assigned to the comparator arm to maintain the blinding of treatment assignment, PK assay results for these patients are generally not needed for the safe conduct or proper interpretation of this study. Sponsor personnel responsible for performing PK assays will be unblinded to patients' treatment assignments to identify appropriate PK samples to be analyzed. Samples from patients who are assigned to the comparator arm will not be analyzed except by request (e.g., to evaluate a possible error in dosing).

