4.6.6 Post Week 76 Efficacy Analyses

The post-Week 76 efficacy analysis will be performed for the patients who meet the adequate response criteria as assessed by investigator at Week 76 and continue blinded treatment after Week 76. An adequate response is present if all of the following criteria are met (REGENCY, Protocol Section 3.1.2):

- UPCR <0.8 g/g or ≥50% reduction in UPCR from baseline to subnephrotic levels (<3 g/g)
- No deterioration in renal function from baseline (eGFR ≥85% of baseline)
- No need for high-dose corticosteroids
- No receipt of rescue therapy or treatment failure

The primary and the key secondary endpoints will be summarized post-Week 76 at Week 106, 132, 158, 184, and 210, by obinutuzumab and placebo groups for the post Week 76 efficacy analysis. This will enable a supportive, exploratory assessment of maintenance of response, acknowledging the limitations of small sample sizes (particularly at later visits), and potential baseline imbalances between groups.

Proportions by treatment groups will be presented for binary endpoints along with difference in proportions between treatment groups, two-sided 95% CI for the difference.

The estimand attributes for the binary endpoints are defined as follows unless otherwise specified:

- Population: Patients with active or active/chronic ISN/RPS 2003 Class III or IV proliferative LN who meet the adequate response criteria at Week 76.
- Endpoint (variable): The primary and key secondary endpoints at Week 106, 132, 158, 184, and 210
- Treatments:
 - Experimental: Obinutuzumab 1000 mg IV infusion start at Day 1 and Week 2,
 24, 26, and either Weeks 50 and 52 or Week 52 only, Week 80 and every
 6 months thereafter until the study unblinded to investigator and patients
 - Control: Placebo
- Intercurrent events: rescue therapy, treatment failure, study treatment discontinuation, death, early study withdrawal, entering into OLT or entering into SFU prior to endpoint assessment.

Rescue therapy, treatment failure, death, early study withdrawal and entering into the OLT will be handled using a composite strategy.

Study treatment discontinuation will be handled using a treatment policy strategy.

Entering into SFU will be handled using a hypothetical strategy targeting an effect that would occur in the hypothetical scenario in which no patient entered into SFU.

Summary measure: Difference in proportions at a specified visit of interest. The

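### Protocol 4.2 and SAP 1.2.1 end the site mask on B-cell, PK, immunoglobulin and ADA results at the Week 76 primary analysis, about a year before Protocol 3.1.5 unblinds investigators

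*Protocol*

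**What the plan says.** Protocol 4.2 states that "site personnel and the Sponsor's staff involved with the conduct of the study will not receive unblinded data related to peripheral B-cell counts, PK results", and the sentence continues through specific "immunoglobulin levels (IgM, IgA), or ADA results during the study, as listed below, until the primary efficacy and safety analyses through Week 76". One end date therefore serves two groups, the sites and the sponsor. SAP 1.2.1 carries the same sentence, ending "specific immunoglobulin levels, or ADA results during the study, as listed below, until the primary efficacy and safety analyses through Week 76"; it does not name IgM or IgA. In neither document does a list follow that would settle which results are covered or for how long.

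Protocol 3.1.5 sets two dates. For the sponsor: "After the primary analysis the Sponsor will be unblinded to treatment assignment". For the sites: "unblinding of investigators and patients will not occur until data is available for all eligible patients through one year of blinded follow-up beyond Week 76". Those data must also have been analysed by then. Protocol 3.1.2 repeats that investigators and patients stay blinded until that event, and Protocol 3.1.4 keeps the blind in place during study follow-up.

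Protocol 4.5.5 adds one rule for one assay: "Flow cytometry results will remain blinded until the study is unblinded".

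For the binary endpoints after Week 76, SAP 4.6.6 says: "Rescue therapy, treatment failure, death, early study withdrawal and entering into the OLT will be handled using a composite strategy".

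**The concern.** Protocol 3.1.5 delays unblinding of sites so that controlled data can be collected beyond Week 76. During that period the investigator judges whether a patient has lost response and may move to open-label obinutuzumab, and that move enters the binary endpoints through the composite strategy. If the same investigator may see results that point to the treatment arm, the comparison is blinded in name only.

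Protocol 4.2 itself treats these tests as potentially unblinding, which is why it withholds them. Its end date is the one that Protocol 3.1.5 gives the sponsor, applied to the sites as well.

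**Working it through.** The check is mainly a comparison of text.

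**1. Dates side by side**

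| Place | Who | What | Until |
|---|---|---|---|
| Protocol 4.2 | Sites and sponsor study staff | B-cell counts, PK, IgM/IgA, ADA | Week 76 primary analysis |
| SAP 1.2.1 | Same | Same, immunoglobulins not named | Week 76 primary analysis |
| Protocol 3.1.5 | Sponsor | Treatment assignment | After the primary analysis |
| Protocol 3.1.2, 3.1.5 | Investigators, patients | Treatment assignment | One further year of blinded follow-up, plus its analysis |
| Protocol 4.5.5 | Not restricted to a group | Flow cytometry | Study unblinding |

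For B-cell counts, 4.2 and 4.5.5 contradict each other directly. For PK, immunoglobulin and ADA results, 4.2 is the only rule, and it ends early.

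**2. Length of the gap.** Both dates run from Week 76 of the last patients. One year more is 76 + 52 = Week 128, and the analysis follows. The first scheduled visit at or after that point is Week 132. The gap is about one year, shifted by the difference between the two analysis times.

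**3. What each result reveals**
- *PK:* Protocol 4.2 says comparator samples are not analysed unless requested. The mere existence of a PK result therefore generally points to obinutuzumab.
- *B-cell counts:* 94% of obinutuzumab patients in the Phase II trial were depleted at Week 52 (Protocol 5.1.1.7). This is highly revealing, but 4.5.5 bars it if that section is followed.
- *IgM and IgA:* at Week 76 of the Phase II trial (Protocol 5.1.1.8), low IgM was seen in 38.6% vs 10.2% and low IgA in 7.0% vs 2.0%. With 1:1 allocation, guessing the arm from the low/not-low status is correct in 0.5 × 0.386 + 0.5 × 0.898 = 64% for IgM and 0.5 × 0.070 + 0.5 × 0.980 = 52.5% for IgA, against 50% by chance. That is weak. Phase II infusions stopped at Week 26, so separation could be larger under continued dosing here.
- *ADA:* the documents give no rates.

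**4. Route to the endpoints.** Protocol Appendix 1, Table 2 continues flow cytometry, PK and ADA sampling at Week 80 and every later blinded visit, and immunoglobulins from Week 106. Protocol 3.1.2 and 3.1.3 make the investigator's view of loss of response the trigger for open-label treatment after Week 80. SAP 4.6.6 counts that entry under the composite strategy.

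**5. How many assessments could be exposed.** Only visits after the primary analysis are at issue. Protocol 3.2 implies about 8 − 5 = 3 years (156 weeks) of enrolment. A Week 106 visit falls after the last patient's Week 76 only for patients enrolled in the final 106 − 76 = 30 weeks; for Week 132 it is the final 56 weeks. The accrual pattern is an assumption:

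| Accrual | Week 106 exposed | Week 132 exposed |
|---|---|---|
| Uniform | 30/156 = 19% | 56/156 = 36% |
| Linearly rising | 1 − (126/156)² = 35% | 1 − (100/156)² = 59% |

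For a given accrual shape these are upper limits, because the primary analysis comes some time after the last Week 76 visit. More back-loaded accrual would raise them.

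**6. Bias.** A bias figure needs the number continuing in each arm, their response rates, how many sites would receive results, and how far behaviour would change. The documents give none of these.

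**The case against.** The strongest reply is that the plan, read as a whole, keeps the sites blinded. Protocol 3.1.2, 3.1.4, 3.1.5 and 4.5.5 all say so, and a footnote to Appendix 1, Table 1 forbids telling site staff B-cell findings from the post-Week 76 biopsy. Protocol 4.2 only stops a prohibition; it does not tell anyone to send results. Entry into open-label treatment also needs loss of adequate response and a need to intensify therapy (3.1.3), with documentation to the Medical Monitor beforehand (3.3.1). A patient in complete renal response meets the UPCR and eGFR parts of adequate response in 3.1.2, so could not normally be moved.

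Much of this stands. The B-cell route is closed if 4.5.5 is followed, and release is permitted rather than planned. A reader might infer that sites will be unmasked, or simulate how many placebo responders would be switched and quote a false-positive rate. The documents support neither: every input to such a simulation would be assumed, it would move patients whom 3.1.3 would not normally admit, and treating all continuing patients as exposed ignores step 5 of the working.

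The reply does not remove the conflict. Protocol 3.1.5 governs treatment assignment and does not mention laboratory results; 4.2 is the section that sets the laboratory rule for sites. A central laboratory could release PK results on the 4.2 date and comply with that section. The Medical Monitor's review is a limited safeguard: the sponsor provides medical monitoring (Protocol 9.5) and is unblinded after the primary analysis, and the documents do not say whether the Medical Monitor stays masked.

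**Conclusion.** The point holds as an inconsistency that should be corrected. For site personnel, the Week 76 end date in Protocol 4.2 and SAP 1.2.1 conflicts with Protocol 3.1.2 and 3.1.5, and for B-cell counts also with 4.5.5. The unprotected results are PK, immunoglobulins and ADA; among them PK is the clear risk.

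What is at stake is limited. SAP 4.6.6 describes the post-Week 76 comparison as exploratory and supportive, plans estimates and confidence intervals without tests, and it lies outside the testing sequence in SAP 2.1.1. A reader might infer that the primary result is compromised; it is not, because the restriction holds until the Week 76 primary and key secondary analyses are done. The size that can be stated is the gap of about one year. The share of visits exposed depends on assumed accrual, and no size of bias can be derived.

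**What to change.** In Protocol 4.2 and SAP 1.2.1, give separate end dates for all the listed results: sponsor staff at the Week 76 primary analysis, and site personnel at study unblinding as defined in Protocol 3.1.5, in line with 4.5.5. Name the immunoglobulins in the SAP as the protocol does. Supply the list that both sentences point to, or delete the reference.

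Reconcile the new wording with Protocol 3.1.4, where the length of follow-up depends on CD19 recovery: while the blind is in place, sites should be told whether follow-up continues without receiving the counts. Such a notice is itself somewhat informative, so the text should say who issues it.

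The cost is a sentence or two in each document and a release setting at the central laboratory. No further patients, samples or analyses are needed.

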3.1.3 Open-Label Treatment

For patients with an inadequate treatment response at Week 76, open-label treatment with obinutuzumab will be provided if all of the following criteria are met at Week 76:

- Inadequate treatment response
- Clinically meaningful improvement from baseline in renal parameters or prior clinically meaningful improvement from baseline followed by worsening
- Need for intensification of therapy
- No unmanageable treatment-emergent adverse events
- No rescue therapy (except corticosteroid-only rescue; see Section 4.4.4.1.1) or treatment failure

Documentation of these criteria will be submitted to the Medical Monitor for review. Investigators may discuss the appropriateness of OLT directly with the Medical Monitor if needed. For patients who initiate OLT based on the Week 76 assessment, the first OLT visit (OLT Day 1) will occur on Week 80.

Additionally, patients who, during blinded treatment after Week 80, experience a loss of adequate response requiring intensification of therapy and without unmanageable treatment-emergent adverse events may initiate OLT once 60 days have elapsed from the most recent obinutuzumab or placebo infusion.

During OLT, patients will receive obinutuzumab 1000 mg on OLT Day 1 and OLT Weeks 2, 24, 26, 52, and once every 6 months thereafter. Background immunosuppression, including doses of corticosteroids and MMF, may be adjusted at the investigator's discretion beginning at OLT Day 1.

During OLT, investigators should regularly review the study safety plan (see Section 5.1), including the risks associated with obinutuzumab (see Section 5.1.1) and management of specific adverse events that may be related to obinutuzumab (see Section 5.1.3.3), to ensure the patient has not developed a condition that would warrant discontinuation of obinutuzumab infusions. Prior to resuming OLT after treatment

interruption, investigators should refer to Section 5.1.3.2 to ensure the patient meets the criteria for resuming treatment.

After study unblinding (see Section 3.1.5), no further OLT will be initiated and ongoing OLT will be discontinued after OLT Week 52. Subsequent access to obinutuzumab may occur through post-trial access (see Section 4.3.4).

Patients who discontinue OLT will enter SFU (see Section 3.1.4).

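### The hold on unblinding laboratory results ends for site staff at the Week 76 primary analysis, about a year before site blinding may end

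*Protocol*

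**What the plan says.** Protocol 4.2 has one sentence for two groups, site personnel and the Sponsor's trial staff. Neither is to receive unblinded "peripheral B-cell counts, PK results, specific immunoglobulin levels (IgM, IgA), or ADA results during the study", and the hold runs "until the primary efficacy and safety analyses through Week 76". SAP 1.2.1 repeats the rule without naming the immunoglobulin classes: "specific immunoglobulin levels, or ADA results during the study, as listed below, until the primary efficacy and safety analyses through Week 76". Both sentences point to a list that should follow, but none does.

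Protocol 3.1.5 treats the two groups differently. For the first: "After the primary analysis the Sponsor will be unblinded to treatment assignment". For sites and patients: "unblinding of investigators and patients will not occur until data is available for all eligible patients" through one more year, and until the analysis of those data is complete. Protocol 3.1.2 likewise keeps investigators and patients blinded until study unblinding while treatment after Week 76 is decided.

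One assay has its own rule. Protocol 4.5.5 states: "Flow cytometry results will remain blinded until the study is unblinded". That covers CD19 counts. It does not cover PK, immunoglobulins or ADA.

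**The concern.** The end date in Protocol 4.2 suits the Sponsor, who is unblinded at the primary analysis. It is wrong for sites, which must stay blinded well beyond it. Once it passes, nothing in either document bars PK, IgM/IgA or ADA results from reaching an investigator who is still treating patients under blind.

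At stake is the controlled comparison after Week 76. After Week 80, whether a patient has lost response and needs intensified therapy is the investigator's opinion (Protocol 3.1.2), and that opinion opens the way to open-label obinutuzumab (OLT). In SAP 4.6.6, OLT entry is handled by the composite strategy for the binary endpoints, so for the response endpoints it counts as non-response. An investigator who infers placebo has a reason to move the patient to open-label drug, and that move would count against the placebo group.

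**Working it through.** The plan gives no figure on this point, so there is none to reproduce. Sample size and power are not involved.

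**Step 1: end dates side by side, for site personnel.**

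| Result | Hold ends (Protocol 4.2, SAP 1.2.1) | Any other rule | Site blinding ends (Protocol 3.1.5) |
|---|---|---|---|
| B-cell counts | Week 76 primary analysis | Section 4.5.5: study unblinding | Study unblinding |
| PK | Week 76 primary analysis | None | Study unblinding |
| IgM, IgA | Week 76 primary analysis | None | Study unblinding |
| ADA | Week 76 primary analysis | None | Study unblinding |

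The first row is a contradiction. The other three are a gap.

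**Step 2: length of the gap.** Site unblinding waits until "data is available for all eligible patients through one year of blinded follow-up beyond Week 76". For the last eligible patient that is Week 76 + 52 = Week 128. Let a1 be the time from the last Week 76 visit to the primary analysis, and a2 the time from the last Week 128 data to completion of the later analysis. The gap is (128 + a2) − (76 + a1) = 52 + (a2 − a1) weeks. If the two analyses take similar time (assumption), it is about 52 weeks.

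**Step 3: the assays continue.** Protocol Appendix 1, Table 2 schedules PK and ADA samples at Week 80 and every later blinded visit, and serum immunoglobulins from Week 106.

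**Step 4: how informative a result is.**

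- PK: under Protocol 4.2, comparator samples are not analysed except by request. The existence of a result therefore points almost directly to obinutuzumab.
- IgM: Protocol 5.1.1.8 gives IgM below 0.4 g/L at Week 76 of the Phase II study in 38.6% (obinutuzumab) and 10.2% (placebo). The likelihood ratio is 0.386 / 0.102 = 3.8.
  - With a prior of 50% for obinutuzumab, one low value gives 0.5 × 0.386 / (0.5 × 0.386 + 0.5 × 0.102) = 79%.
  - If patients continuing under blind split 50:30, borrowing the planned response rates as an assumption, the prior is 0.50 / 0.80 = 62.5% and the result is 86%.
  - A value that is not low says less. The probabilities become 41% and 53%.
- ADA: the documents give no rates, so its strength cannot be quantified here.

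**Step 5: which decisions fall after the hold ends.** The primary analysis needs every patient to have completed Week 76 or withdrawn, with cleaned data (SAP 4). Decisions on adequacy of response at Week 76 are therefore already made. Protocol 3.2 gives about 8 years in total and about 5 after the last enrolment, hence roughly 3 years (156 weeks) of accrual. Under uniform accrual (assumption), when the last patient reaches Week 76 the median patient is near Week 76 + 78 = 154 and the first near Week 76 + 156 = 232. Much of the Week 106 to 210 data would be collected while the hold still applies. What remains exposed is loss-of-response and OLT-entry decisions taken after the primary analysis.

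**The case against.** The strongest reply is that this is a wording slip. Protocol 4.2 says when a restriction ends and does not tell anyone to send results to sites. Protocol 3.1.2 and 3.1.5 state plainly that sites stay blinded, and the sentence in 4.2 may simply have the Sponsor in mind. This stands in part: there is no planned unblinding. But the sentence names site personnel, the SAP repeats it, and for three of the four result types no other text corrects it.

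Four stronger readings are tempting, and the documents do not support them:

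- **That the plan releases unblinding data to sites.** It does not. A safeguard lapses while the duty to stay blinded continues.
- **That B-cell counts measure the exposure.** Protocol 5.1.1.7 reports 94% depletion at Week 52 in the Phase II study, so a count looks decisive. Section 4.5.5 protects flow cytometry until study unblinding. A footnote to Protocol Appendix 1, Table 1 also keeps B-cell-related biopsy findings from sites. The 94% would matter only if Section 4.2 overrode Section 4.5.5.
- **That every post-Week 76 endpoint is exposed.** Step 5 shows otherwise. Renal response also rests on central-laboratory UPCR and creatinine, and for eGFR and FACIT-F change SAP 4.6.6 handles OLT entry by treatment policy.
- **That an unblinded Medical Monitor will steer OLT entry.** Protocol 3.1.3 says "Investigators may discuss the appropriateness of OLT directly with the Medical Monitor if needed", and Section 3.1.5 unblinds the Sponsor without naming exceptions. Neither document says that the Medical Monitor receives treatment codes. How the Sponsor separates its own staff is an operational choice.

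It is also fair that SAP 4.6.6 calls the later comparison supportive and exploratory and plans confidence intervals without tests, and that the testing sequence in SAP 2.1.1 contains no post-Week 76 endpoint.

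**Conclusion.** The end date is wrong for site personnel as written. For PK, IgM/IgA and ADA the hold ends about 52 weeks before site blinding may end, assuming similar analysis times at the two points. For B-cell counts two protocol sections contradict each other. The results concerned are informative: a PK result nearly identifies obinutuzumab, and one low IgM value moves an even prior to 79%, if the Phase II rates carry over to this trial's longer dosing.

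The consequence is limited to investigators' decisions on loss of response and OLT entry made after the primary analysis, and through them to the exploratory comparison in SAP 4.6.6. The size of any bias cannot be calculated, because it depends on results actually reaching sites and on how investigators would act on them. The Week 76 primary result, its power and the Week 76 adequacy decisions are untouched. The change is still worth making, because it closes a route to bias at almost no cost.

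**What to change.** In Protocol 4.2 and SAP 1.2.1, replace the single end date with two, applying to every listed assay (B-cell counts, PK, IgM/IgA, ADA): the primary analysis for the Sponsor, and study unblinding as defined in Section 3.1.5 for site personnel. Make Section 4.5.5 refer to the same rule, use the same immunoglobulin wording in both documents, and either supply the list that both sentences announce or delete the reference to it. Emergency unblinding stays as it is.

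The cost is protocol and SAP wording plus data-access settings for these results. No visit, sample, analysis or sample size changes. A formal separation of the Medical Monitor from unblinded Sponsor staff is not part of this fix.
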